##### **4.1. Inclusion Criteria**

Subject eligibility should be reviewed and documented by an appropriate member of the investigator's study team before subjects are included in the study.

Subjects must meet all of the following inclusion criteria to be eligible for enrollment in the study:

1. Evidence of a personally signed and dated informed consent document indicating that the subject (or a legally acceptable representative/parent(s)/legal guardian) has been informed of all pertinent aspects of the study.
2. Males  $\geq 18$  and  $< 65$  years of age.
3. Body Mass Index (BMI)  $\geq 17.5$  and  $\leq 30.5$  kg/m^2 and total body weight  $\geq 50$  and  $\leq 100$  kg.
4. Diagnosis of severe hemophilia A or B (Factor VIII or Factor IX activity  $\leq 1\%$ ).
5. Subjects enrolled as Factor VIII or Factor IX inhibitor patients must have a positive inhibitor test result (above the upper limit of normal) at the local laboratory and must receive a bypass agent as primary treatment for bleeding episodes. A positive inhibitor test result will be above the upper limit of normal for the assay. Inhibitor test results from up to 6 months prior to Day 1 may be used to meet this requirement.
6. Patients with an episodic (on-demand) treatment regimen prior to Screening, who are willing and able to washout from Factor VIII (for at least 72 hours) or Factor IX (for at least 96 hours) replacement therapy, or bypass agent therapy (for rFVIIa and APCC: at least 72 hours), prior to Screening laboratory assessments of factor activity and have no plans to institute prophylactic factor treatment during the study period.

7. Had at least 6 acute bleeding episodes (spontaneous/traumatic) during the 6-month period prior to Screening. Surgical bleeding episodes do not apply to this criterion.
8. If receiving therapy for human immunodeficiency virus (HIV) or active hepatitis infection, have stable disease and be on a stable regimen at the time of study entry (ie, stable dosing for at least 3 months before consent).
9. Willing and able to comply with scheduled visits, treatment plan, laboratory tests, and other study procedures.
10. If with partners currently pregnant or if able to father children, agree to use a highly effective method of contraception throughout the study and for least 28 days after the last dose of investigational product.

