5.1. Hypotheses and Decision Rules

Prophylactic treatment with PF-06741086 will be considered superior to On Demand treatment with respect to ABR reduction if 1) the upper limit of the 2-sided 80%CI of the ratio of ABR in PF/historical On Demand is <1 and 2) the estimate of the ratio of ABR in PF/historical On Demand ≤ 0.3 . Drug will be considered not superior to On Demand treatment if the lower limit of the 2-sided 80%CI of the ratio of PF/historical On Demand >0.3 .

The primary efficacy endpoint in the four dose cohorts will be tested in a hierarchical order to control the overall family-wise error rate. The efficacy test will first be performed in the dose cohort with the highest PK exposure (eg, C_{trough} and/or AUC) that is proven to be safe and tolerated. If the result is significant, the ABR will be tested against the historical On Demand group in the dose cohort with the next highest PK exposure. The test procedure will continue until the dose cohort with the lowest PK exposure is tested against the historical On Demand group.

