5.2.3. Analyses for Count Data

Separate models will be run for each pairwise comparison between the historical control group and each dose cohort. The frequency of bleedings will be analyzed using a negative binomial model. Log transformed duration of time on study will be included as an offset variable in the model.

Sample SAS codes are provided as follows:

```
PROC GENMOND Data=sample;
  Where dose='300mg SC';
  Class trt;
  Model count=trt/dist=negbin link=log offset=logtime alpha=0.2 ;
  Estimate 'PF-06741086 - PCB' trt 1 -1;
  Estimate 'PF-06741086' intercept 1 trt 1/alpha=0.2;
  ods output ParameterEstimates=pvalue estimates=est;
```

Run;

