6.2. Secondary Endpoint(s)

6.2.1. Efficacy Endpoint

6.2.1.1. Statistical Analysis

The efficacy analysis will be conducted in the PPAS. A historical On Demand group will be constructed using the following internal Pfizer studies: ReFacto AF 3082B2-4432 (B1831004), BeneFIX B1821010, and BeneFIX 3090A1-400 (B1821004). Subjects who are on On Demand treatment in B1831004, as well as data from the On Demand period in B1821004 and B1821010 will be used to construct the historical On Demand group. The resulting dataset will be further filtered to match the key inclusion/exclusion criteria of B7841002 based on age and factor activity ($18 \leq \text{age} \leq 65$ and factor activity $\leq 1\%$). Outliers with extremely high ABR will be removed from the pooled On Demand group, if appropriate. All resulting subjects will be included in the historical control group.

The frequency of bleedings will be analyzed using a negative binomial model as detailed in Section 5.2.3. The ratio of ABR and its 80% 2-sided CI in the PF-06741086 arm versus that in the historical On Demand group will be generated for each dose cohort. The corresponding p-value will also be presented. Model based ABR and its 80%CI will be generated for each dose cohort.

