6.2.1.2. Descriptive Summary

Descriptive statistics of ABR (n, mean, median, standard deviation, minimum and maximum) will be generated by dose level and cohort for both the treatment period and the 6 months prior to study enrolment. ABR from the historical On Demand group will also be presented. It may take time for the inflammation in the joints to settle, and thus the number of bleeding episodes during the first month post-dose may be higher than the last two months on drug. In order to investigate whether the ABR decreases over time, the ABR in the PF-06741086 arm will be summarized by study month and dose level and cohort. Two bar graphs will be generated presenting mean and median ABR by study month, respectively. The ABR during the 6 months prior to study enrolment will be plotted together with the on-study ABR. All dose cohorts as well as the historical On Demand group will be presented on the same plot.

In addition, ABR will also be summarized for hemophilia A and hemophilia B subjects separately, if applicable.

If the analysis of PD biomarker data shows that with increasing dose levels, the PD effect reaches plateau, ABR from different dose levels may be pooled together and analyzed against the historical On Demand group.

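### If on-demand bleed rates differ between hemophilia A and B, the treatment-only comparison lets an A/B imbalance between cohort and historical pool bias the ratio behind the superiority rule

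*SAP*

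**What the plan says.** **The pool.** SAP 6.2.1.1 takes On Demand data from three named internal studies, one of ReFacto AF (B1831004) and two of BeneFIX (B1821010 and B1821004). The data are "further filtered to match the key inclusion/exclusion criteria of B7841002 based on age and factor activity". Extreme outliers may be dropped, and then: "All resulting subjects will be included in the historical control group". Hemophilia type is not used to select, match or weight.

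**The model.** SAP 5.2.3: "Separate models will be run for each pairwise comparison between the historical control group and each dose cohort". The sample code is "Model count=trt/dist=negbin link=log offset=logtime alpha=0.2", so treatment is the only regressor beside the log-time offset.

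**The rule.** SAP 5.1 calls the drug superior if "the upper limit of the 2-sided 80%CI of the ratio of ABR in PF/historical On Demand is <1" and the estimated ratio is at most 0.3. It is not superior if the lower 80% limit exceeds 0.3. Cohorts are tested in sequence, starting from the highest exposure.

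**The trial side.** Protocol 4.1 admits severe hemophilia A or B. Protocol 3, 3.1 and 5.1 state no quota or stratum by type within a cohort.

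**Where type does appear.** SAP 6.2.1.2: "ABR will also be summarized for hemophilia A and hemophilia B subjects separately, if applicable". Protocol 9.2.1 makes an evaluation by factor deficiency optional, and SAP 6.4.1 counts A and B subjects per cohort. The Wilcoxon sensitivity test in SAP 6.2.1.3 is not stratified by type.

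**The concern.** The comparison is not randomised. A treatment-only model cannot separate a drug effect from a difference in case mix between cohort and pool. With 6 subjects, one subject moves a cohort's mix by 17 percentage points, and the four cohorts can have four different mixes set against the same pool.

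The ratio feeds a stated decision rule. Because testing is hierarchical, a distorted ratio in the highest-exposure cohort also decides whether the other cohorts are tested. The optional pooling across doses in SAP 6.2.1.2 would use the same control group. The Wilcoxon test shares the weakness, so it cannot reveal it. The separate A and B summaries could show an imbalance but do not correct the ratio.

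**Working it through.** **1. The plan's own figure.** Inputs from Protocol 9.1: 2.36 bleeds per patient-month, 3 months, 6 subjects, 85% reduction, one-sided alpha 0.1, Poisson. Expected bleeds per subject are 2.36 × 3 = 7.08 for controls and 0.15 × 7.08 = 1.062 on treatment. The control group size is not stated; 6 is a cautious choice.

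SE of the log ratio = √[1/(6 × 1.062) + 1/(6 × 7.08)] = 0.425. Power = Φ(1.897/0.425 − 1.282) = 99.9%. The stated figure of more than 80% therefore holds as a lower bound. It uses one control rate, not split by type.

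**2. Size of the bias.** Let r be the B:A on-demand rate ratio, c the share of type B in the cohort, p the share in the pool, and R the true within-type treatment ratio. With a log link, treatment only and equal follow-up, the model estimates R × b, where

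b = (1 − c + c·r) / (1 − p + p·r).

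The documents give none of r, c or p. Assumed ranges: r 0.5 to 2.0, p 33% to 67%, c 0% to 33%. The widest factors arise at c = 0 and p = 0.67, where b = 1/(0.33 + 0.67r):

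| r | b | 0.15 becomes | True ratio behind an estimate of 0.30 |
|---|---|---|---|
| 0.5 | 1.50 | 0.225 | 0.20 |
| 0.7 | 1.25 | 0.19 | 0.24 |
| 1.0 | 1.00 | 0.15 | 0.30 |
| 1.4 | 0.79 | 0.12 | 0.38 |
| 2.0 | 0.60 | 0.09 | 0.50 |

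A milder case is a cohort with 1 of 6 type B and a pool 50% type B. Then b = (0.833 + 0.167 × 1.5)/(0.5 + 0.5 × 1.5) = 0.87 at r = 1.5, and 1.13 at r = 0.67. A cohort with more type B than the pool reverses the direction.

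**3. Effect on the decision.** Assume 50 controls and dispersion k (k = 0 is Poisson). SE = √[(1/(7.08·R·b) + k)/6 + (1/7.08 + k)/50]. In every case below the point-estimate criterion is the binding one, so P(success) = Φ(ln(0.3/(R·b))/SE). For R = 0.15, b = 1.50 and k = 0: SE = √(0.628/6 + 0.141/50) = 0.328, and Φ(0.288/0.328) = 81%.

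| True R | b | P(success), k = 0 | P(success), k = 1 |
|---|---|---|---|
| 0.15 | 1.00 | 96% | 88% |
| 0.15 | 1.25 | 91% | 80% |
| 0.15 | 1.50 | 81% | 70% |
| 0.30 | 0.79 | 77% | 67% |
| 0.30 | 1.00 | 50% | 50% |
| 0.30 | 1.25 | 19% | 33% |
| 0.40 | 0.79 | 43% | 46% |
| 0.40 | 1.00 | 12% | 28% |
| 0.40 | 1.25 | 1% | 15% |

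**4. What adjustment does.** Negative binomial simulation, 1,500 runs. Assumptions: cohort 5 type A and 1 type B, pool of 50 with 30% type A, k = 0.5 treated as known.

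- r = 1.5, true ratio 0.40: both criteria are met in 48% of runs unadjusted and 30% with a type covariate. With equal rates the unadjusted figure is 27%.
- r = 0.67, true ratio 0.30: 35% unadjusted and 53% adjusted.
- The covariate raises the SE of the log ratio from 0.42 to 0.44.

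**The case against.** A reader might infer that the pool certainly mixes types and that any imbalance passes straight into the ratio. The documents do not support that. They name products, not the hemophilia type of each source study. They give no bleed rate by type, and with equal rates there is no bias at all. A reader might also infer that the whole test is against 0.3. In fact the upper confidence limit is compared with 1; 0.3 applies to the point estimate and to the bound for not superior.

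Other fair points:

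- The extremes of 0.60 and 1.50 come from one corner of assumed inputs: an all-A cohort, a pool two-thirds B and a two-fold rate difference. At the planned ratio even 1.50 gives 0.225, below 0.3. This stands.
- Trial subjects need at least 6 bleeds in the previous 6 months (Protocol 4.1), and the pool filter names no such criterion. That selection compresses type differences in the cohort. With 2.36 bleeds per month in type A and assumed dispersion of 0.5 to 1.0, a B:A ratio of 0.5 becomes about 0.61 to 0.62, and 2.0 becomes about 1.7 to 1.8. A type effect estimated mainly from controls need not carry over exactly. This stands as a limit on any adjustment.
- If product determines type, type coincides with source study among the controls. The type term then also absorbs differences between studies, so the cost is more than one degree of freedom. This stands.
- Efficacy is a secondary aim, and the Protocol Summary plans no formal hypothesis. Each cohort's A/B counts and prior 6-month bleeding rate will also be shown. These soften the point, but SAP 5.1 still sets a decision rule on the uncorrected ratio.

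**Conclusion.** The point holds conditionally. The plan pools controls without regard to type, lets type vary freely within cohorts, and bases its rule on a treatment-only ratio. If on-demand rates differ by type, an A/B imbalance biases that ratio in a direction and by an amount the documents cannot settle. The ranges in the working rest on assumed rates and mixes, and on the inference from product names that both types are in the pool.

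The planned ratio of 0.15 is fairly safe. True ratios of about 0.25 to 0.5 are exposed, because a modest factor there moves the estimate across 0.3 either way. The sponsor holds the historical data and can check the rates by type. This is a worthwhile improvement to the analysis, not evidence that the comparison is wrong.

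**What to change.** In SAP 5.2.3 and 6.2.1.1, before database lock:

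- Prespecify a type-adjusted ratio for each cohort, with hemophilia type (A or B) as a covariate in the negative binomial model. SAP 6.1 already derives type for trial subjects; confirm that it is available for the pool.
- Repeat the comparison with historical controls restricted or weighted to the cohort's A/B mix.
- Report A/B counts for each cohort and for the pool.
- State whether the SAP 5.1 conclusion holds under adjustment.
- Present the model-based ABR at the cohort's own A/B mix, by weighting the predicted rate for each type. The mix matters only for this figure: in a main-effects log-link model the ratio does not depend on it. The sample code's estimate of the cohort rate would need type coefficients.

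An all-A or all-B cohort can still be adjusted, because the controls estimate the type effect. A cohort-by-type interaction is not realistic with 6 subjects.

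Cost: slightly wider intervals (about 5% on the log scale, 0.44/0.42, under the simulated inputs). If type coincides with source study among the controls, the type term also carries study differences, and the report must say so.

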6.2.1.2. Descriptive Summary

Descriptive statistics of ABR (n, mean, median, standard deviation, minimum and maximum) will be generated by dose level and cohort for both the treatment period and the 6 months prior to study enrolment. ABR from the historical On Demand group will also be presented. It may take time for the inflammation in the joints to settle, and thus the number of bleeding episodes during the first month post-dose may be higher than the last two months on drug. In order to investigate whether the ABR decreases over time, the ABR in the PF-06741086 arm will be summarized by study month and dose level and cohort. Two bar graphs will be generated presenting mean and median ABR by study month, respectively. The ABR during the 6 months prior to study enrolment will be plotted together with the on-study ABR. All dose cohorts as well as the historical On Demand group will be presented on the same plot.

In addition, ABR will also be summarized for hemophilia A and hemophilia B subjects separately, if applicable.

If the analysis of PD biomarker data shows that with increasing dose levels, the PD effect reaches plateau, ABR from different dose levels may be pooled together and analyzed against the historical On Demand group.

6.2.1.3. Sensitivity Analysis

An exact Wilcoxon-rank sum test will be utilized to test the difference in ABR between active treatment and historical On Demand group. A one sided p-value <0.1 will be considered as statistically significant. The same hierarchical approach as described in [Section 5.1](#) will be used for multiplicity control.

6.2.2. Pharmacokinetic Endpoints

PK parameters for PF-06741086 will be listed and summarized for subjects in the PK Parameter Analysis Set (as defined in [Section 4.4.2](#)) by dose level and cohort and study day as shown in the following table:

Table 2. PK Parameters to be Summarized Descriptively for PF-06669571 and L-DOPA by Day

Dose	Parameter	Summary Statistics
Single Dose (Day 1 to Day 7 QW or Day 1 to Day 28 QM)	AUC_{last} , C_{168h} (Day 1 to Day 7 QW), C_{672h} (Day 1 to Day 28 QM), C_{max}	N, arithmetic mean, median, cv%, standard deviation, minimum, maximum, geometric mean and geometric cv%.
Single Dose (Day 1 to Day 7 QW or Day 1 to Day 28 QM)	T_{max}	N, median, minimum, maximum.
Multiple Dose (Day 29 to Day 36 (QW) or Day 29 to Day 57 (QM))	$C_{max, ss}$, $AUC_{t, ss}$ (for IV administration only), CL (for IV administration only), CL/F (for SC administration only), C_{min}	N, arithmetic mean, median, cv%, standard deviation, minimum, maximum, geometric mean and geometric cv%.
Multiple Dose (Day 29 to Day 36 (QW) or Day 29 to Day 57 (QM))	$T_{max, ss}$	N, median, minimum, maximum.

There will be 1 summary table presenting all PK parameters. This will include data from both routes of administration. The treatment subheading will include the route of administration and dose information.

6.2.2.1. Statistical analyses of PK Concentrations

Presentations for PF-06741086 concentrations for subjects in the Concentration Analysis Set (as defined in [Section 4.4.1](#)) will include:

- A listing of all concentrations sorted by dose level and cohort, subject ID, day, nominal time post-dose, and actual times. Deviations from the nominal time will be given in a separate listing;
- A summary of concentrations by dose level and cohort, day and nominal time post-dose, where the set of statistics will include n, mean, median, standard deviation, coefficient of variation (cv%), minimum, maximum and the number of concentrations above the lower limit of quantification;

- Median concentrations time plots (on both linear and semi-log scales) against nominal time post-dose by dose (all doses on the same plot per scale, based on the summary of concentrations by dose and time post-dose);
- Mean concentrations time plots (on both linear and semi-log scales) against nominal time post-dose by dose level and cohort (all doses on the same plot per scale, based on the summary of concentrations by dose and time post-dose);
- Individual concentration time plots by dose level and cohort (on both linear and semi-log scales) against actual time post-dose (there will be separate spaghetti plots for each dose per scale).

The length of time used for the x-axes of these plots will be decided on review of the data, and will depend on how long PF-06741086 concentration is quantifiable above the limit of quantification in the matrix.

For summary statistics, median and mean plots by sampling time, the nominal PK sampling time will be used, for individual subject plots by time, the actual PK sampling time will be used.

6.2.3. Pharmacodynamic Endpoints

Endpoints:

- Total TFPI;
- Thrombin generation (lag time, peak thrombin generation, and endogenous thrombin generation potential);
- PF1+2;
- D-dimer;
- dPT;
- Analysis time window: Day 1 up to Day 113;
- Analysis population: Pharmacodynamic Analysis Set (defined in [Section 4.5](#));
- Analysis methodology: Change from baseline will be analyzed using the MMRM model (detailed in [Section 5.2.4](#)). Change from baseline will also be analyzed using a four parameter Emax model. The detailed Emax modeling will be described in a separate PK/PD plan. Subjects with detectable FVIII activity (hemophilia A) or FIX activity (hemophilia B) at the time of a PD specimen collection may have result(s) for the respective PD parameter censored from the PD analysis.

Reporting results:

- Raw data: For each endpoint of interest, the number of subjects, mean, median, standard deviation, geometric mean, geometric coefficient of variation (cv%), minimum, and maximum, will be summarized by dose level and cohort and study day;
- Change from baseline: the number of subjects, mean, median, standard deviation, geometric mean, geometric coefficient of variation (cv%), minimum, and maximum, will be summarized by dose level and cohort and study day. Baseline is defined in [Section 3.2.3](#). The model based mean and 80% two sided CI will be presented by dose level and cohort and study day.

Figures:

- Median pharmacodynamic endpoint time plots against study day by dose level and cohort (all doses on the same plot, based on the summary of pharmacodynamic endpoint by dose and study day). The plot will be generated for absolute value as well as the change from baseline value. Two sets of plots will be produced, with the x-axis being on nominal and semi-log scales, respectively.
- Mean pharmacodynamic endpoint time plots against study day by dose level and cohort (all doses on the same plot, based on the summary of pharmacodynamic endpoint by dose and study day). The plot will be generated for absolute value as well as the change from baseline value. Two sets of plots will be produced, with the x-axis being on nominal and semi-log scales, respectively.
- Individual pharmacodynamic endpoint time plots against study day by dose level and cohort (there will be separate spaghetti plots for each dose). The plot will be generated for absolute value as well as the change from baseline value.
- The model based mean and 80% two sided CI from the MMRM model will be plotted against study day. All dose cohorts will be presented on the same plot with one line representing one dose cohort.

CCI

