### 5.7.2. Treatment(s) for Acute Bleeding Episodes

If a subject experiences an acute bleeding episode at any point throughout the study, the subject is to be stabilized utilizing the subject's standard hemostatic treatment regimen

(which may include Factor VIII or Factor IX replacement therapy, or rFVIIa bypass agent therapy at approximately 90 µg/kg per dose). Pausing or withdrawal of treatment with investigational product is not required in the event of a breakthrough bleed, but may be considered at the discretion of the investigator. See [Section 7.2.5](#) for additional information.

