## 7.1. Safety

### 7.1.1. Laboratory Tests

The following safety laboratory tests will be performed at times defined in the **STUDY PROCEDURES** section of this protocol. Additional laboratory results may be reported on these samples as a result of the method of analysis or the type of analyzer used by the clinical laboratory; or as derived from calculated values. These additional tests would not require additional collection of blood. Unscheduled clinical labs may be obtained at any time during the study to assess any perceived safety concerns.

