**Table 5. Laboratory Tests**

Hematology	Chemistry	Urinalysis	Other
Hemoglobin Hematocrit RBC count Platelet count WBC count Total neutrophils (Abs) Eosinophils (Abs) Monocytes (Abs) Basophils (Abs) Lymphocytes (Abs)	BUN/urea and Creatinine Glucose (fasting) Calcium Sodium Potassium Chloride Total CO 2 (Bicarbonate) AST, ALT Total Bilirubin Alkaline phosphatase Uric acid Albumin Total protein	pH Glucose (qual) Protein (qual) Blood (qual) Ketones Nitrites Leukocyte esterase Urobilinogen Urine bilirubin Microscopy a	Factor V Leiden mutation b Prothrombin 20210 Mutation b HBs Ag b Total HbcAb b HCVAb b HIV b Anti-thrombin III Protein C activity b Protein S level b PT/INR aPTT Fibrinogen Cardiac Troponin I Factor VIII c Factor IX c Factor VIII and Factor IX inhibitor d Lipid profile b CD4 cell count b
	Additional Tests (Needed for Hy's law)		
	AST, ALT (repeat) Total bilirubin (repeat) Albumin (repeat) Alkaline phosphatase (repeat) Direct bilirubin Indirect bilirubin Creatine kinase GGT PT/INR		

- Only if urine dipstick is positive for blood, protein, nitrites or leukocyte esterase.
- At Screening only.
- At Screening and Day 1 only.
- Only At Screening and only for subjects with hemophilia history of inhibitors, if necessary. Inhibitor test results from up to 6 months prior to Day 1 may be used to meet requirement.

Any remaining serum/plasma from samples collected for clinical safety labs at baseline and at all times post-dosing may be retained and stored for the duration of the study. Upon completion of the study, retained safety samples may be used for the assessment of CCI [REDACTED] samples to be used for this purpose will be packaged and shipped to Pfizer's BioBank for storage. These data will not be included in the clinical study report. Samples will be retained in Pfizer's Biobank for up to 1 year following completion of the study.

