#### **7.2.5. Treatment of Bleeding Episodes**

Bleeding episodes that occur during this study may be treated (on-demand) with hemostatic therapy (eg intravenous factor products or rFVIIa bypass agent therapy at approximately 90 µg/kg) as deemed appropriate by the investigator. The specific treatment with hemostatic therapy is at the discretion of the subject/caregiver/investigator, but all doses of hemostatic therapy taken after signing of informed consent will be documented as concomitant medications or concomitant treatments.

If a subject experiences a bleeding episode during the washout period preceding screening laboratory assessments, the subject is to be stabilized utilizing the subject’s usual hemostatic treatment regimen. Once the bleeding episode has been successfully treated a new washout period should be completed prior to obtaining the screening laboratory tests.

If a subject experiences a bleeding episode during the washout period preceding the initial administration of PF-06741086 the subject is to be stabilized utilizing the subject’s usual hemostatic treatment regimen and a new washout period should be implemented. Once treatment of the bleeding episode with hemostatic agents has been completed a new washout period should be initiated in anticipation of the initial treatment with PF-06741086.

If a subject experiences a bleeding episode during the PK assessment period following administration of PF-06741086, the subject is to be stabilized utilizing the subject’s usual factor VIII or factor IX treatment regimen or rFVIIa bypass agent therapy at approximately 90 µg/kg, and protocol specified observations and procedures should proceed to completion. Pausing or withdrawal of treatment with investigational product is not required in the event of a breakthrough bleed, but may be considered at the discretion of the investigator.

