**Table 6. Blood Volume for SC Cohorts**

Sample Type	Sample Volume (mL)	Number of Sampling Times			Total Volume (mL)
		Screening	Study Period	Follow-Up	
Safety Labs					157
Serum chemistry (with Lipid profile a )	5	1	7	1	45
Hematology	3	1	7	1	27
Prothrombin 20210 mutation	3	1	0	0	3
Factor V Leiden mutation testing	3.5	1	0	0	3.5
aPTT, PT/INR, Anti-thrombin III b , Factor VIII and Factor IX activity c , Fibrinogen, Protein C a , Protein S a , D-dimer, PF1+2 (PD samples) [Single combined sample]	4.5	1	11	1	58.5
Serology (HBs Ag, HBc Ab, HCV Ab, and HIV)	5	1	0	0	5
Cardiac Troponin I d	3	0	5	0	15
PK	4.5	0	11	1	54
Immunogenicity (ADA, NAb)	9	0	5	1	54
PD (note some PD assayed from safety samples)					106.8
TFPI level	2.7	0	11	1	32.4
TGA	3.5	0	11	1	42
dPT	2.7	0	11	1	32.4
Factor VIII and Factor IX inhibitor a	4.5	1	0	0	4.5
CCI [REDACTED]	[REDACTED]	[REDACTED]	[REDACTED]	[REDACTED]	[REDACTED]
Banked biospecimens	4	0	1	0	4
TOTAL					393.8

a at Screening only.

b at Screening and Days 1, 8, 15, 22 and 29 only.

c at Screening and Day 1 only.

d at Days 1, 8, 15, 22 and 29 only.

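### The SAP's rule for censoring PD results depends on a factor activity value that the visible protocol plans only at Screening and Day 1, and it does not name rFVIIa; a flag based on recorded bleed treatment should replace or supplement it.

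*SAP*

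**What the plan says.** **The rule.** SAP 6.2.3 analyses change from baseline in each PD endpoint, Day 1 to Day 113, by MMRM and by an Emax model that a separate PK/PD plan describes. It adds an optional exclusion. The trigger is worded as "Subjects with detectable FVIII activity (hemophilia A) or FIX activity (hemophilia B) at the time of a PD specimen collection"; the stated consequence for them is that they "may have result(s) for the respective PD parameter censored from the PD analysis". It gives no cut-off for *detectable* and names no one to decide.

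**The assay schedule.** Protocol Table 5 restricts Factor VIII and Factor IX with the footnote "At Screening and Day 1 only". Table 6 says the same ("at Screening and Day 1 only"), as does Table 7. Table 1 marks factor activity at Screening and Day 1 and leaves Days 2 to 29 blank. Table 2 (Day 30 to Day 113) has no such row, and the visit lists in Protocol 6.2.2 to 6.3.1 do not include the test. Protocol 7.1.1 leaves one opening: "Unscheduled clinical labs may be obtained at any time during the study to assess any perceived safety concerns".

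**Bleed treatment on study.** Protocol 7.2.5: "Bleeding episodes that occur during this study may be treated (on-demand) with hemostatic therapy". Protocol 5.7.2 describes the subject's standard regimen, "which may include Factor VIII or Factor IX replacement therapy, or rFVIIa bypass agent therapy". Protocol 7.2.5 also has the scheduled procedures carry on when a bleed is treated during the PK assessment period.

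**The records.** Protocol 5.7 requires start and stop dates for concomitant treatments. Protocol 7.2.1 and 7.2.5 require hemostatic therapy to be documented as concomitant treatment.

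**The concern.** The SAP accepts that circulating factor can make a PD result unsuitable for analysis, then ties the remedy to a measurement that is not planned when it would be needed. After Day 1 the rule has no systematic input. The SAP shows no substitute: the PD analysis set (SAP 4.5) and Protocol 9.4 contain no exclusion for hemostatic treatment.

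The rule is also incomplete. Subjects with inhibitors may have bleeds treated with rFVIIa, which a FVIII or FIX activity trigger does not name. SAP 6.5.1 already reports the type and dose of bypass agent around thrombotic events, so the SAP makes use of these data elsewhere.

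Three things are at stake:

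- **PD time course and dose response.** With 6 subjects per cohort, one or two samples drawn after factor or rFVIIa could show in a cohort-by-day mean.
- **The plateau judgement in SAP 6.2.1.2.** If PD appears to level off with dose, ABR may be pooled across dose levels and compared with the historical group.
- **Discretion.** The study is open-label and sponsor-open (Protocol 3 and 9.7). Under an optional rule with no cut-off, results could be removed after they have been seen.

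**Working it through.** **1. Count the PD visits and compare them with the assay schedule.** Tables 1 and 2 mark PD on Days 1, 2, 4, 8, 15, 22, 29, 30, 33, 57, 85 and 113, which is 12 visits. Table 6 plans 11 study-period draws plus 1 follow-up draw for TFPI: 2.7 mL × 12 = 32.4 mL, as printed. For thrombin generation, 3.5 mL × 12 = 42 mL, also as printed. Planned factor activity coincides with a PD draw once, pre-dose on Day 1. After Day 1, 0 of 11 PD visits has a planned value.

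**2. Illustrate how many samples fall near a treated bleed.** This counts samples; it does not measure bias. It is limited to Days 2 to 85: 10 visits × 24 subjects = 240 samples.

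Inputs:
- Historical rate 2.36 per patient-month (Protocol 9.1): 2.36 × 12 = 28.32 per year.
- 85% reduction (Protocol 9.1): 28.32 × 0.15 = 4.248 per year. 70% reduction (the 0.3 ratio in SAP 5.1): 28.32 × 0.30 = 8.496 per year.
- On-study bleed frequency counts bleeds treated with intravenous factor or bypass agents (Protocol 7.2.1), so the rate serves as a treatment rate.
- Windows of 72 h and 96 h, borrowed from the washouts in Protocol 4.3. 120 h is an assumption for records that hold dates only.

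Assumptions: one infusion per counted bleed, bleeds independent of visit timing, the same window for all subjects, and no treatment in the washout before Day 1.

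Per sample: p = 1 − exp(−rate × min(window, hours since the Day 1 dose) / 8766), where 8766 = 365.25 × 24. Day 2 is capped at 24 h and Day 4 at 72 h.

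At 4.248 per year, p is 0.01156 (24 h), 0.03429 (72 h), 0.04546 (96 h) and 0.05649 (120 h). At 8.496 per year it is 0.02299, 0.06740, 0.08884 and 0.10979.

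| Reduction | Window | Sum of p over 10 visits | × 24 | Share of 240 |
|---|---|---|---|---|
| 85% | 72 h | 0.01156 + 9 × 0.03429 = 0.3202 | 7.7 | 3.2% |
| 85% | 96 h | 0.01156 + 0.03429 + 8 × 0.04546 = 0.4095 | 9.8 | 4.1% |
| 85% | 120 h | 0.01156 + 0.03429 + 8 × 0.05649 = 0.4978 | 11.9 | 5.0% |
| 70% | 72 h | 0.02299 + 9 × 0.06740 = 0.6296 | 15.1 | 6.3% |
| 70% | 96 h | 0.02299 + 0.06740 + 8 × 0.08884 = 0.8011 | 19.2 | 8.0% |
| 70% | 120 h | 0.02299 + 0.06740 + 8 × 0.10979 = 0.9687 | 23.2 | 9.7% |

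**3. Spread over subjects.** At 85% this is about 1.9 to 2.5 samples per 6-subject cohort for 72 to 96 h (7.7 / 4 and 9.8 / 4). The windows, with overlaps merged, cover 600 h (72 h) or 744 h (96 h) per subject. Then 1 − exp(−4.248 × 600 / 8766) = 25.2% and 1 − exp(−4.248 × 744 / 8766) = 30.3%, or 6.1 to 7.3 of 24 subjects with at least one such sample.

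**The case against.** **PD is secondary and the numbers are small.** This stands. The protocol plans no formal hypothesis test, SAP 6.2.3 already includes medians and individual plots that limit or expose a few odd values, and each cohort's ABR is compared with the historical group whatever PD shows. Pooling under SAP 6.2.1.2 is optional.

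**The rule might still be usable.** Unscheduled tests are allowed, and Protocol 7.1.1 also allows extra results from samples already drawn. PD handling text is redacted, and the PK/PD plan was not available. A reader might infer that the rule can never be applied; the documents do not support that. They show only that no value is planned after Day 1, and that unscheduled tests are offered for safety concerns.

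**The evidence on rFVIIa is indirect.** Also correct. Protocol 1.2.1 reports that the study drug improved thrombin generation in plasma dosed with rFVIIa. A reader might take this as proof that rFVIIa alone moves the PD markers, but it does not say so. The number of subjects with inhibitors is not given, so the rFVIIa gap cannot be sized separately.

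**The link to neutralizing antibodies is weak.** Agreed. SAP 6.5.7.1 needs treatment-emergent NAb on at least 2 determinations plus loss of effect on at least 2 of 3 markers, one of which is total TFPI. This route is minor.

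**Day 113 should not inflate the count.** It is left out. It falls 35 days after the last SC dose and 56 after the last IV dose, outside the active treatment period used in SAP 6.5.7.1, and says little about a dose plateau.

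**Conclusion.** The point holds in a limited form. The only PD censoring rule visible in the SAP relies on a test with no planned value at any of the 11 PD visits after Day 1, and it does not name one permitted bleed treatment. As written, affected coagulation PD results would generally stay in the MMRM, and removals would be discretionary. The main consequence is for the PD time-course and dose-response summaries and for the plateau judgement; the primary safety endpoints are untouched.

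On Days 2 to 85, about 3% to 4% of samples would follow bleed treatment closely at the planned 85% effect and 6% to 8% at 70%, rising to about 5.0% and 9.7% with a 120 h window. These figures rest on planning bleed rates and on borrowed windows that were not validated for PD.

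A reader might go further and conclude that the PD results will be biased, or that a false plateau will be declared. The documents do not say how far an infusion moves each marker, so neither conclusion is supported. Confidence is moderate because of the redactions and the unseen PK/PD plan.

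**What to change.** Amend SAP 6.2.3 before database lock:

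1. Replace or supplement the activity trigger with a mandatory flag on coagulation PD results (thrombin generation, PF1+2, D-dimer, and dPT if justified), driven by recorded FVIII, FIX, rFVIIa or any APCC treatment.
2. Use product-specific analysis windows that the sponsor justifies, counted in calendar days where only dates exist. The 72 h and 96 h washouts are a possible default for analysis, but they are eligibility rules.
3. Keep total TFPI, which Protocol 1.3.1.3 describes as reflecting target binding.
4. Present the MMRM with and without flagged results. State in advance which is primary and which informs the plateau judgement in SAP 6.2.1.2.
5. Apply the same flag in the PK/PD plan unless it already has one.
6. If the activity trigger is kept, define *detectable* (eligibility allows activity up to 1%) and schedule the assay. Table 6 already assigns factor activity to the tube that serves "D-dimer, PF1+2 (PD samples) [Single combined sample", so no new tube type is needed. The protocol schedule would have to change, and rFVIIa would still need the treatment records.

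**Cost.** SAP wording and simple programming on data already collected. The analysis without flagged results loses the shares shown above, and more from subjects who bleed more. That strains the missing-at-random assumption in SAP 5.3.3, which is why the analysis with all results should stand beside it. Windows that are too long drop unaffected samples, and windows that are too short keep affected ones.
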